#### **4.4. Handling of Subject Withdrawals or Subject Discontinuation of Clinical Trial Intervention**

Subjects that are dropped from the clinical trial prior to administration of the interventional investigational product or whom fail to achieve intraoperative complete retinal reattachment will be considered screen failures and will not be enrolled or included in analysis.

Subjects who have retinal detachment within 1-week post-operatively will be deemed to have failed Day 0 (day of surgery) and will be removed from the efficacy analysis. These will be considered “dropped” subjects.

Any subject receiving the investigational product will be followed for safety throughout the scheduled course of the clinical trial, or until the subject has reached a status of un-reachable.

It is anticipated that there will be a potential drop-out rate of up to 20%. To assure the clinical trial meets the required approximate 100 evaluable eyes for analysis, additional subjects may need to be enrolled to meet this goal.

#### **4.5. Premature Termination or Suspension of Clinical Trial**

In the event of premature termination or suspension of clinical trial, the subject will continue to follow with his/her surgeon as part of their standard of care management.

### **5. INVESTIGATIONAL TREATMENT**

**Product Name:** ADX-2191 (methotrexate 0.8%) for intravitreal injection.

#### **5.1. Description of Investigational Product**

Methotrexate is an antimetabolite and antifolate drug that has been used for cancer treatment since the 1950s. The drug was originally approved in 1959 and is now available generically. It

has exceptionally well-understood biological and clinical effects. Methotrexate is currently FDA-approved for oral administration and for intravenous, intramuscular, intrathecal, or intra-arterial injection. Approved indications include psoriasis, rheumatoid arthritis, and certain neoplastic diseases. Other mechanisms of action involve direct effects on inflammatory pathways, in particular neutralization of the effects of TNF- $\alpha$  and IL-1 $\beta$ , though the molecular mechanisms underlying these effects remain largely uncharacterized.

Several case series have been published using intravitreal injections of methotrexate, most commonly for intraocular lymphoma. (Frenkel et al., 2008; Hardwig, Pulido, & Bakri, 2008; Hardwig, Pulido, Erie, Baratz, & Buettner, 2006; Samson, Waheed, Baltatzis, & Foster, 2001)

## 5.2. Packaging and Labeling

ADX-2191 drug product is formulated as a sterile and aqueous solution for intravitreal delivery. The drug product will be supplied in single-dose, 2 mL glass vials with a 0.5 mL fill volume.

The quantitative composition of the ADX-2191 drug product are presented in Table 2.

## 5.3. Investigational Product Storage

The Investigational Product (IP) must be stored in a secure area accessible only to the investigator and his/her designees. The IP will be administered only to subjects entered into the clinical trial, in accordance with the conditions specified herein.

The subject kit label will include, but not limited to, the following information:

- trial protocol number
- contents
- subject number and initials (manually recorded)
- storage conditions

- Investigational New Drug statement
- Sponsor's name, address, and phone number

The vial label will be included, but not limited to, the following information:

- trial protocol number
- contents
- storage conditions
- Investigational New Drug statement
- manufacturer name and address
- Sponsor name, address, and phone number

#### **5.4. Investigational Product Dosage, Preparation, and Administration**

Proposed dosage of ADX-2191: 400 µg in 0.05 mL intravitreal injection

ADX-2191 will be provided as the investigational product to clinical trial sites that have obtained IRB approval. The IP will be supplied in single-use vials. ADX-2191 should be withdrawn from the vial into an appropriate syringe allowing excess volume to accommodate needle fill if the needle will be exchanged. Used vials/syringes should be disposed of appropriately in accordance with local policy which may include use of yellow "chemo waste" bags.

It is preferred that the ADX-2191 be drawn into the syringe at time of administration, however, if local policy requires the IP to be drawn up in the pharmacy, this is acceptable as long as all sterility guidelines are met. Appropriate destruction and documentation of any IP must be completed.

Administration of ADX-2191 is described in Section 6.11. Refer to the Pharmacy Manual for additional details.

#### **5.5. Investigational Product Accountability**

The IP is to only be prescribed by the principal investigator or his/her named sub-investigator(s) and is only to be used in accordance with this protocol. The IP must be distributed only to subjects properly qualified under the conditions specified herein.

The investigator or designated qualified site staff is responsible for monitoring the inventory of IP and for the accountability of all used and unused IP received from the supplier. This includes the amount of IP dispensed to subjects, and the amount returned or disposed upon the completion of the trial. Inventories must be carefully and accurately documented according to applicable state, federal, and local regulations, current Good Clinical Practices (GCPs), including the International Council for Harmonisation (ICH) guidelines, and clinical trial procedures. IP accountability will be available for Sponsor's review and will be verified by the clinical trial monitor during site visits and at the completion of the trial.

At the conclusion of the trial, IP reconciliation will be performed, and all remaining IP not returned to the sponsor, will be destructed and disposed of according to clinical site's SOP. Sponsor will be provided with a final accounting of IP for approval prior to destruction.

The investigator or designated qualified site staff will maintain accurate records of receipt and condition of IP, including dates of receipt, and temperature log of storage conditions. In addition, accurate records will be kept of the date of IP administration and the subject to whom IP was administered. Any reasons for departure from the protocol-specified dispensing regimen must also be recorded.

## **5.6. Investigational Product Retention**

IP must be retained until completion or termination of the clinical trial, and written authorization from the Sponsor has been received. All unused and used IP drug should be destroyed at the site or returned to the distributor, as specified by Sponsor. It is the investigator's responsibility to ensure that the Sponsor has provided written authorization prior to return or destruction, and that appropriate records of the disposal are documented and maintained. No used or unused IP may be disposed until fully accounted for by the clinical trial monitor.

## **5.7. Subject Compliance with Investigational Product Administration**

Compliance or product administration will be assessed through accurate medication administration records maintained at the clinical sites. The investigator/or appropriately licensed designee will administer the investigational product as defined in the protocol administration schedule. IP compliance will be assessed through review of the subject's medical record.

## **5.8. Subject Compliance with Clinical Trial Intervention**

Protocol compliance will be assessed at each clinical trial visit. Compliance information will be collected from the medical/research record and reported via an eCRF. This information will be reviewed by the clinical trial monitor in accordance with the Monitoring Plan.

## **5.9. Assessment of Clinician and/or Subject Compliance with Clinical Trial Procedural Intervention**

Clinician/subject compliance will be assessed at each clinical trial visit. Compliance information will be collected from the medical/research record and reported via a case report form. This information will be reviewed by the clinical trial monitor in accordance with the Monitoring Plan.

## **5.10. Concomitant Therapy and Procedures**

The use of any concomitant medication, prescription or over the counter, taken within 30 days prior to signing consent, is to be recorded on the source document and corresponding electronic eCRF along with the reason the medication was taken.

Concurrent enrollment (within 90 days of enrollment) in another investigational drug or medical device clinical trial is not permitted.

## **5.11. Prohibited Concurrent Therapies and Procedures**

Prohibited medications, treatments, and procedures during the clinical trial are outlined in the Exclusion Criteria (Section 3.6.2).

## **6. CLINICAL TRIAL PROCEDURES**

Clinical trial assessments and evaluations should be performed by the investigator and/or qualified site staff according to Schedule of Events and Assessments (Table 1). Refer to the Clinical Trial Activities Schedule (Section 7).

### **6.1. Informed Consent**

Informed consent forms must be approved for use by the reviewing Institutional Review Board (IRB)/Research Ethics Board (REB)/Independent Ethics Committee (IEC). Informed consent must be obtained for all subjects participating in the clinical trial prior to performing any procedures. The informed consent process must be adequately documented in the source records.

### **6.2. Eligibility Review**

The investigator or qualified site staff will confirm that all inclusion and exclusion criteria have been met. Per screening evaluations, all subjects will require a confirmation from the CRC and Medical Monitor that they meet the retinal imaging inclusion criteria to be eligible. If urgent (<24 hours) CRC verification is required, the Medical Monitor may unilaterally review the images and authorize the planned enrollment. In the event there is a discrepancy between the CRC and Medical Monitor review, the Medical Monitor determination will be the study accepted reading of accountability.

### **6.3. Demographics, Medical History, and Social History**

Demographic information to be captured include subject initials (where locally permitted), date of birth (alternatively year of birth, if full date of birth is not allowed to be collected for legal reasons), age, sex, race, and ethnicity will be obtained from the subject and recorded in the eCRF.

Medical and social history will be recorded in the eCRF. Current underlying conditions, including conditions diagnosed within the last 30 days of consent, which may have resolved before screening, must be recorded.

### **6.4. Physical Examination**

A physical examination will be performed including, but may not be limited to, an evaluation of the cardiovascular, gastrointestinal, respiratory and central nervous systems at Screening. Additional examinations may be obtained on Principal Investigator's discretion. The physical examination may be performed by any medically qualified physician or certified PA, whether part of the study team or not, as long as documentation of the required examination is available. The ophthalmic examinations must be performed by a member of the study team.

### **6.5. Concomitant Medications**

Concomitant medications used 30 days prior to consent to treat any medical conditions will be recorded in the eCRF. Any changes in dosage or new medications added must be recorded in the

subject eCRF. The Sponsor and investigator or qualified site staff will review and evaluate concomitant medication usage on an ongoing basis.

## **6.6. Adverse Events**

Any serious, unexpected adverse events (AE) believed to be due to the intervention rather than the natural disease process will prompt a filing of an adverse event form with the local IRB office and the FDA.

AEs will be collected from the time the subject signs the informed consent form through 30 days after the last dose of IP. AEs must be recorded in the eCRF. The Sponsor and investigator or qualified site staff will review and evaluate AEs on an ongoing basis. See Section 8 for further detail on AE reporting.

## **6.7. Safety Testing**

Samples of blood and urine will be collected for clinical laboratory tests which includes general safety parameters (hematology, serum chemistry, and urinalysis) and pregnancy. All subjects will provide blood samples for clinical laboratory testing for chemistry and hematology, as well as urine for a urinalysis at Screening Visit (Visit 1) and Final Visit (Visit 16 / Week 24; or at subjects last visit when subject is terminated and follow up is not available through Week 24, if possible).

Chemistry profile includes blood urea nitrogen (BUN), calcium, chloride, creatinine, creatinine to BUN ratio, carbon dioxide (CO2), potassium, sodium, albumin, alanine aminotransferase (ALT), alkaline phosphatase (ALP), Aspartate aminotransferase (AST), total bilirubin, and total protein.

Hematology profile includes hematocrit, hemoglobin, platelets, red blood cells, and white blood cells (without differentials).

For women of childbearing potential (WOCBP) enrolled in the Intervention cohort, a pregnancy test will be collected at the Screening Visit (Visit 1), and prior to each injection of ADX-2191, through Visit 16 / Week 24. Results must be available and confirmed to be negative before the subject may be enrolled in the clinical trial. IP must be discontinued for any subject with a positive pregnancy test result.

## **6.8. Ophthalmic Examinations**

### **6.8.1. Best-Corrected Visual Acuity**

BCVA will be collected at Screening (V1), Day 1 (V3), Weeks 1 (V4), 4 (V7), 8 (V11), 12 (V13), 16 (V15), and 24 (V16). The BCVA will be measured using ETDRS chart by masked technicians at a standard photopic light level of at least 85 cd/m^2. These assessments are to be conducted in both eyes at Visit 1(screening) and Visit 16 (end of study/early termination). The study eye only may be examined at other time points.

### **6.8.2. Intraocular Pressure**

IOP will be collected at Screening (V1), Day 1 (V3), Weeks 1 (V4), 4 (V7), 8 (V11), 12 (V13), 16 (V15), and 24 (V16).

### **6.8.3. Clinical Ophthalmic Examination**

Routine full ophthalmic, dilated follow-up exams will be performed on Screening (V1), Day 1 (V3), Weeks 1 (V4), 4 (V7), 8 (V11), 12 (V13), 16 (V15), and 24 (V16) by the Treating Investigator. This exam is inclusive of a slit lamp exam. Additional follow-up exams may be scheduled by the Treating Investigator at his or her discretion.

### **6.8.4. Endpoint Evaluation**

It is preferred that an evaluating investigator assess whether the primary endpoint has been met at the pre-specified evaluation timepoints Weeks 1 (V4), 4 (V7), 8 (V11), 12 (V13), 16 (V15), and 24 (V16). If an evaluating investigator is not available, the Treating Investigator may determine whether the primary endpoint has been met. The primary endpoint requires verification by the CRC before recurrent retinal detachment reoperation. In cases where CRC verification is not possible due to technical limitations with the Optical Coherence Tomography or fundus photograph, then the evaluating investigator will contact the trial medical monitor to confirm whether the primary endpoint has been met. Regardless, SD-OCT and wide-field imaging will be collected and verified by the CRC when the endpoint has been met, or at conclusion of the clinical trial, whichever is sooner.

### **6.8.5. Color Fundus Photographs**

All subjects will undergo pre-operative color widefield, 4-field or standard 7-field retina photos. Photos will be interpreted as per reading center protocol with masked readers. Pre-operative anterior segment photos are also preferred, if possible. In cases where preoperative color photography is technically difficult for image acquisitions (i.e. dense lens opacity, constricted pupil, intraocular bleeding, etc.), then intraoperative imaging using the operative microscope is allowed.

The CRC and Medical Monitor will review the pre/intraoperative photos and approve all subjects prior to their planned enrollment. If urgent (<24 hours) CRC verification is required, the Medical Monitor may unilaterally review the images and authorize the planned enrollment. Fundus Photographs will be collected at Screening, (V1; with the exception of subjects with OGIs and retinal detachment; or subjects who require intraoperative photos as stated above), Day 1 (V3), Weeks 1 (V4), 4 (V7), 8 (V11), 12 (V13), 16 (V15), and 24 (V16). The CRC will certify all imaging technicians.

### **6.8.6. Macular Spectral-Domain Optical Coherence Tomography (SD-OCT)**

Macular SD-OCT imaging may be done using Heidelberg Spectralis or Zeiss Cirrus (Spectralis imaging is preferred if available). SD-OCTs will be interpreted as per CRC protocol with masked readers. Note that subjects should be imaged consistently with the same SD-OCT machine if multiple machines are available in the same facility.

SD-OCT will be collected at Screening (V1), Day 1 (V3), Weeks 1 (V4), 4 (V7), 8 (V11), 12 (V13), 16 (V15), and 24 (V16).

## 6.9. Pars Plana Vitrectomy

All subjects will receive Pars Plana Vitrectomy (PPV) in the usual manner on Day 0 (V2). The PPV will be performed under local or general anesthesia using a small gauge system (23, 25, or 27 gauge) at the discretion of the investigators.

Investigators will agree to observe the following principles:

1. Lens status:

If Phakic:

1. If phakic with a clear lens, the lens may be preserved
2. If lensectomy is performed, a complete capsulectomy is required
3. Cataract extraction with implantation of a posterior intraocular lens is permitted

If Pseudophakic:

1. May keep intraocular lens (IOL), or may remove IOL and capsular bag at surgeon discretion

If Aphakic:

1. May not insert secondary IOL at time of re-detachment surgery
2. Epiretinal, subretinal, and epiciliary membranes will be removed at the discretion of the investigator, including anterior vitreous base dissection when indicated.
3. Use of intravitreal triamcinolone, chemical dyes including indocyanine green and brilliant blue, relaxing retinectomy, scleral buckle, and perfluorocarbon liquid will be used as needed at the discretion of the investigator.
4. Intraoperative triamcinolone to identify tissue planes/vitreous is acceptable, but an additional injection in or around the eye at the end of surgery is not permitted.
5. If retinectomy is performed, removal of the anterior retina is strongly encouraged.
6. Moderate to intense white laser retinopexy burns will be used to seal any retinal breaks. 2-3 laser rows as per the investigator's usual routine but an additional row of laser burns is recommended. No cryopexy may be used.
7. Silicone oil 1000 or 5000 centistokes will be used as the preferred tamponade.
8. The injection is given into the oil bubble as the last step of the procedure before suturing the sclerotomies. Subjects that will receive the alternative option of ADX-2191 on Day 1 (Visit 3) will be given injection into the oil bubble following the required safety assessment.
9. No subconjunctival, peribulbar, intravenous, oral, or sustained-release intraocular steroids will be used. Topical ophthalmic steroid eye drops, or ointment may be used per surgeon's usual routine. If patient is already on oral steroids for a different condition, this may be continued at the same dose or less.

10. All subjects receiving the investigational product will be required to aggressively use lubricating drops and/or ointment at least four times daily.
11. Silicone oil removal is required after Week 24.

Investigators will have discretion regarding the need for re-operation. Indications for re-operation may include endophthalmitis and recurrent retinal detachment, as defined in Section 3.6. Silicone oil cannot be removed within the 24-week trial period, unless for the above indications.

Recurrence of retinal detachment requiring a return to the operating room will prompt cessation of any further intravitreal injections and only Routine Surgical Care will be provided. Subjects will be followed through the Week 24 assessment visit.

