### **3.2.2. Randomization**

Per screening evaluations, all subjects will require a confirmation from the CRC and Medical Monitor that they meet the retinal imaging inclusion criteria to be eligible. If urgent (<24 hours) CRC verification is required, the Medical Monitor may unilaterally review the images and authorize the planned enrollment. In the event there is a discrepancy between the CRC and Medical Monitor review, the Medical Monitor determination will be the study-accepted reading of accountability. In Part 1a, eligible subjects are randomized to either standard procedure or standard procedure with intervention. This randomization is a 1:1 ratio within the stratified cohort groups. In Part 1b, subjects must still meet all inclusion criteria prior to enrollment. This verification process provides an additional level of objectivity in assuring subject qualification for participation in the clinical trial. If the photographic image is too poor in quality to verify eligibility, then the subject will be noted as screen failures. As noted in Section 6.8.5, in cases where preoperative color photography is technically difficult for image acquisitions (i.e., dense lens opacity, constricted pupil, intraocular bleeding, etc.), then intraoperative imaging using the operative microscope is allowed.

In Part 1a, those subjects that meet enrollment criteria will enter the randomization process and will be allocated to the Control vs. Intervention cohorts. The assignment to cohort will be

revealed intraoperatively at the conclusion of the surgery to the investigator after retinopexy has been applied. Note: administratively, the randomization may occur prior to surgery if logistically required by the site. However, the investigator must remain blinded to randomization until the defined timepoint. When administrative randomization occurs prior to surgery, all measures must be taken to avoid indicating assigned treatment group prior to conclusion of surgery.

Randomization scheme will be managed by an Interactive Response Technology (IRT) system. Subjects will be randomized by indication (recurrent retinal detachment due to PVR or any RD associated with OGI).

Eligible subjects will be randomized 1:1 intraoperatively to either group:

**Control:** Standard Procedures

**Intervention:** Standard Procedures with the addition of repeated intravitreal injections of ADX-2191 until post-operative Week 16.

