### **9.4.4. Demographic and Baseline Medical History**

The demographic and baseline medical history data, obtained at screening, will be summarized descriptively. For quantitative variables, the summaries will include the number of observations, mean, standard deviation, median, minimum, and maximum. Qualitative variables will be summarized using counts and percentages.

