#### **9.4.6. Secondary Efficacy Analyses**

The logistic regression model will be used to assess the superiority of ADX-2191 over standard-of-care in reducing the rate of recurrent retinal detachment. The covariate-adjusted difference in rate of recurrent retinal detachment and associated 95% CI will be summarized (Ge et al., 2011). The model will include a binary response variable (indicating recurrence of detachment or not), a treatment effect and stratification factor adjustment.

The secondary endpoint of the Best Correct Visual Acuity (BCVA) of change from level at Screening (Visit 1) to the level at Week 24 will be analyzed using an MMRM model. The MMRM model will be fit with Screening BCVA value, treatment, visit, and the interaction of treatment and visit. Change from Screening level of BCVA will be the dependent variable.

Subgroup analysis for BCVA will be conducted based on the following factors, if deemed necessary:

1. Lens status (phakia vs. aphakia vs. pseudophakia)
2. Prior recurrent retinal detachments ( $>3$  vs.  $\leq 3$ )
3. Longstanding retinal detachment ( $>1$  month) (yes vs. no)
4. Pre-operative macular scar or macular hole (yes vs. no)

Exploratory efficacy endpoints will be summarized by visit for descriptive statistics only. No statistical between-group comparison will be performed, unless otherwise specified.

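### The BCVA model in 9.4.6 has no term for lens status at the end of the Day 0 operation, although 6.9 leaves the lens to the surgeon; in the randomized comparison this costs precision but does not cause bias

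*Combined protocol and SAP*

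**What the plan says.** **Lens handling on Day 0 (Section 6.9).** For phakic eyes: "If phakic with a clear lens, the lens may be preserved"; "If lensectomy is performed, a complete capsulectomy is required"; and "Cataract extraction with implantation of a posterior intraocular lens is permitted". For pseudophakic eyes the surgeon "May keep intraocular lens (IOL), or may remove IOL and capsular bag at surgeon discretion". Aphakic eyes may not receive a secondary lens at this operation, so replacement does not arise there.

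**The endpoint (Sections 2.2.2 and 9.4.6).** BCVA change runs from the pre-operative Screening visit to Week 24, so the operation lies inside the interval.

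**The model (Section 9.4.6).** "The MMRM model will be fit with Screening BCVA value, treatment, visit, and the interaction of treatment and visit". It has no lens term and no stratification factor.

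**The subgroup (Section 9.4.6).** The first factor listed for BCVA is "Lens status (phakia vs. aphakia vs. pseudophakia". The subgroup analyses are to be run only if judged necessary, and the lens factor is not tied to a time before or after surgery.

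**Assignment.** The Part 1a strata are clinical presentation and number of recurrent detachments (Section 3.1), not lens status. Assignment in Part 1a is "revealed intraoperatively at the conclusion of the surgery to the investigator after retinopexy has been applied" (Section 3.2.2). Section 6.10 adds that the surgeon stayed blinded until then, even where randomization was done administratively before surgery. From Version 5.0 (Part 1b) there is no randomization and every eye is treated.

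**The concern.** Removing or replacing a lens can change acuity whatever the drug does. Two eyes with the same Screening acuity, one losing an opaque lens on Day 0 and one keeping its lens, need not have the same expected change at Week 24, so Screening BCVA cannot fully stand in for what was done to the lens. The plan treats lens status as relevant to BCVA, since it lists it first among the subgroup factors, but it does not use it in the overall contrast.

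Three things are at stake: the width of the BCVA interval; a chance difference in lens mix between the Part 1a groups, which the model cannot correct; and, if Part 1b eyes are compared with Part 1a controls, a possible systematic difference in lens procedures. The undated subgroup is a smaller matter of the same kind. If it were built on Screening status, an eye whose cataract was removed on Day 0 would be grouped with eyes that kept their lens.

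**Working it through.** **The plan's own figure.** No SD, effect size or power is stated for BCVA. The only power statement (Section 9.3.1) concerns detachment: rates 0.2 and 0.5, two-sided 0.05, 45 per group, about 80%. It reproduces. The uncorrected formula gives 39 per group and the continuity-corrected formula 45, with power at 45 per group of 80.1% (81.5% by Fisher's exact test). The present point does not touch it.

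**Assumed inputs, because the documents give none.**
- L: difference in mean BCVA change between two lens groups, in units of the residual SD with Screening BCVA and lens in the model; range 0.3 to 1.0.
- p: share of eyes in one of the two lens groups; range 0.2 to 0.5.
- n: 50 per arm, the synopsis target for Part 1. The number actually randomized in Part 1a is not stated.

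**Precision.** Without the lens term the residual variance is multiplied by 1 + L²p(1−p), and the interval width by its square root.

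**Chance imbalance.** The SD of the shift in the contrast is L × √(2p(1−p)/n).

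| L | p | Variance factor | Interval wider by | SD of chance shift, n = 50 |
|---|---|---|---|---|
| 0.3 | 0.2 | 1.0144 | 0.7% | 0.024 SD |
| 0.3 | 0.5 | 1.0225 | 1.1% | 0.030 SD |
| 0.5 | 0.2 | 1.0400 | 2.0% | 0.040 SD |
| 0.5 | 0.5 | 1.0625 | 3.1% | 0.050 SD |
| 1.0 | 0.2 | 1.1600 | 7.7% | 0.080 SD |
| 1.0 | 0.5 | 1.2500 | 11.8% | 0.100 SD |

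The percentage widening does not depend on n.

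**Power illustration.** With an assumed treatment effect of 0.5 SD, 50 per arm and p = 0.5, power with the lens term is 70.5%. Without it, power is 69.6% (L = 0.3), 67.9% (L = 0.5) or 60.9% (L = 1.0).

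**If non-randomized eyes contribute.** The shift is L × the difference in lens-group share between the compared groups: 0.3 × 0.10 = 0.03 SD at the low end and 1.0 × 0.30 = 0.30 SD at the high end. The 10- to 30-point differences are assumed.

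**Parameter count.** Section 6.8.1 gives seven post-baseline BCVA visits (Day 1 and Weeks 1, 4, 8, 12, 16, 24). A lens main effect costs 1 parameter at two levels or 2 at three. Adding a lens-by-visit interaction and a separate removal indicator brings the three-level version to 2 + 2×6 + 1 = 15, and the two-level version to 1 + 6 + 1 = 8. Part 1 targets about 100 evaluable eyes in all.

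**The case against.** The strongest reply is that an unadjusted model in a randomized comparison is valid, only less efficient. That stands. A reader might infer from Section 6.9 that lens surgery biases the randomized BCVA contrast. Sections 3.2.2 and 6.10 do not support this, because the surgeon is kept blind until the end of the operation.

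Other parts of the reply:

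- *Lens is not unique.* Membrane removal, retinectomy and scleral buckling are also discretionary in 6.9. Prior detachments, detachment duration and macular scar or hole are listed with lens status in 9.4.6 and are also absent from the model. This stands as a limit on emphasis: the number of prior detachments, a Part 1a stratification factor, has at least as good a claim. It is not a reason to leave lens status out.
- *Screening BCVA may absorb part of the lens effect, and acuity is best-corrected.* This is fair. It is why L is defined after adjustment for Screening BCVA and why its range starts low.
- *Part 1b.* Section 9.4.6 does not say whether those eyes enter the BCVA contrast, and no section suggests that knowing the eye will be treated alters lens choice. If it did, lens status would itself follow from allocation, and adjusting for it would not be straightforward. Nor would a lens term remove other differences between non-randomized groups.
- *Screening-based subgroup.* A reader might infer from Section 9.4.4 ("The demographic and baseline medical history data, obtained at screening, will be summarized descriptively") that the subgroup uses Screening status. That section covers demographics and medical history and does not mention lens status. The supportable statement is that the time point is missing.
- *The SAP may settle it.* Sections 9.4.1 and 9.4.9 defer to the SAP. No text more detailed than Section 9 was available for this review, so 9.4.6 is the specification that can be judged.

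**Conclusion.** The gap is real and modest. A discretionary lens procedure falls between the two BCVA readings, the BCVA model omits it, and the optional lens subgroup is undated. In randomized Part 1a the consequence is lost precision and uncorrected chance imbalance: intervals about 1% to 12% wider, with the upper end needing a lens effect of a full residual SD and an even split of eyes. At an intermediate effect of 0.5 SD the widening is 2% to 3%. Every magnitude rests on assumed values.

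Confounding arises only if Part 1b eyes are used in the contrast and lens procedures differ between the groups. A lens covariate would then help only in part.

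A reader might also infer that the covariate would deal with cataract that develops after Day 0. It would not. That is a post-treatment event in eyes that kept their lens, and no section gives an analysis rule for it.

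BCVA is a secondary endpoint, and Section 9.4.3 limits formal testing to one hypothesis, on detachment, so the trial's main conclusion is unaffected.

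**What to change.** In Section 9.4.6 and the SAP, before database lock:

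1. Add lens status at the end of the Day 0 operation to the BCVA MMRM as a main effect: phakic versus not phakic, or three levels if numbers allow.
2. Define the lens-status subgroup by that same end-of-surgery variable. The slit-lamp examination already scheduled for Day 1 (Section 6.8.3) can confirm it.
3. Put the lens-by-visit interaction and a separate indicator for lens or IOL removal in a sensitivity analysis only, because together with three-level status they bring the count to 15 parameters.
4. Do not describe the covariate as handling cataract that arises after Day 0.

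The cost is wording plus one or two degrees of freedom in the main model. If aphakic eyes are few, pool them with pseudophakic eyes. No surgical instruction in Section 6.9 needs to change.
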